## Double Blind Trial Investigating the Role of Sulfasalazine in Decreasing Opioids Requirements in Breast Cancer Patients

History will focus on symptoms of porphyria, intestinal, urinary obstruction, or blood dyscrasias.

- Neuro exam Mini mental state test
- Abd exam Light and deep palpation of the abdomen
- CBC Complete blood count with differential
- BMP Basic metabolic panel with renal function
- LFT Liver function tests
- UA Urinalysis

Finally, blood and urine samples to monitor for side effects from the study medication. The manufacturer of sulfasalazine recommends that blood test be done every two weeks to monitor for side effects. Sulfasalazine may cause anemia and decreased white blood cells. Additionally, it may cause liver and renal damage. Therefore, blood and urine will be collected at every follow up by a phlebotomist who is not part of the study. The collected samples will be labeled by the research team. The blood sample will be used for safety monitoring by analyzing the basic metabolic panel and complete blood count. At the baseline, Week-6, and Week-12, additional blood will be immediately centrifuged and the plasma will be stored in a -80 degrees Celsius freezer for later analysis for inflammatory mediators and tumor markers. The collected urine will be used for urinalysis. Any significant deviation from the baseline values of the CBC, liver function, renal (basic metabolic panel) function, or UA will result in un-blinding of the effected patient, withdrawal from the study, and consultation with the appropriate service.

Patients will be given four paper surveys to assess for pain level, pain medication use, and quality of life. We will utilize a modified pain assessment questionnaire which is used in our pain clinic to assess for pain intensity, frequency, duration, ability to fall and stay asleep, and ability to exercise, this will be completed weekly. We will also utilize the Brief Pain Inventory (short form) for additional pain assessment. The Brief Pain Inventory (BPI) is a valid, clinically useful pain assessment tool that has been used extensively in people with cancer. Its purpose would be to assess the severity of pain and the impact of pain on daily functions. It includes a diagram to note the location of pain, questions regarding pain intensity (current, average, and worst using a 0 to 10 rating scale), and items that evaluate impairment due to pain. This would be used to assess their pain in a systematic approach. The short form survey should take about 5 minutes and will be administered at study entry and end of study. There is no scoring algorithm but the arithmetic mean of the four severity items can be used as measures of pain severity and the arithmetic mean of the seven interference items can be used as a measure of pain interference.

We will use the EORTC QLQ-C30 survey which assess global improvement in the quality of life. The EORTC QLQ-C30 version 3.0 will be used to assess quality of life. The questionnaire is multidimensional in structure, brief and easy to complete, and applicable across a range of

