## **Double Blind Trial Investigating the Role of Sulfasalazine in Decreasing Opioids Requirements in Breast Cancer Patients**

### **Brief Summary**

Cancer pain in general, and cancer-induced bone pain in particular, is a significant health problem in the USA and the rest of the world. With the improvement of new surgical approaches and chemotherapies to treat manage cancer, the number of patients with cancer are now living longer. This great achievement created an unexpected problem. For some cancer patients with bone metastases, pain is worse than the cancer itself. The golden standard to manage cancer-induced bone pain is opioids. Patients with cancer-induced bone pain are now taking ever-increasing doses of opioids to control their pain. Sadly, opioids come with significant side effects. These side effects limit the amount of opioids that can be safely administered. Many attempts have been tried to create better regiments for pain control to lower the need for opioids. There has not been significant success in that area. A better approach to better control cancer-induced bone pain and lower the amount of opioids used would be to add a non-opioid agent that has a different mechanism of action(s). This may create synergism to better control pain while lowering the doses of opioids needed and lowering side effects. Sulfasalazine poses such quality. It is an anti-inflammatory drug with established safety profile. It has been in use for over fifty years for the treatment of inflammatory conditions such as rheumatoid arthritis. In addition to its anti-inflammatory characteristics, sulfasalazine has the capacity in decrease the survival of cancer cells and also to lower the amount of inflammatory mediators released by cancer cells. In short, sulfasalazine inhibits the influx of cysteine into cancer cells and the efflux of glutamate from cancer cells. Cysteine is needed for cell survival against oxidative stress, while glutamate activate pain receptors. Therefore, sulfasalazine will act as anti-inflammatory, an agent to accelerate cancer cells death, and decreasing the released glutamate which activate pain receptors. This one agent with three mechanisms of actions may lower the amount of opioid needed for cancer patients with cancer-induced bone pain while maintaining or improving their pain control. Lowering of opioid dosing may also decrease the side effects associated with opioid use which in turn may improve their quality of life. The objective of this clinical trial is to co-administer sulfasalazine with opioids to patients with cancer-induced bone pain and characterize their pain and their opioid use. Our hypothesis is that adding sulfasalazine to the pain medication regimen will lower the amount of opioids used and lower the side effects. This may improve the quality of life for cancer-induced bone pain patients and decrease the risks of using high amount of opioids for the patients, their families, and society in general. The primary objective of this study is to decrease the amount of opioid pain medication use after addition of sulfasalazine for 12 weeks while controlling pain. The secondary objective is to decrease the intensity of pain and increase the quality of life.

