The patients will return to the pain clinic or the oncology clinic for follow ups at 2 weeks (+/- 1 week), 4 weeks (+/- 1 weeks), 6 weeks (+/- 1 weeks), and 8 weeks (+/- 1 week), 10 weeks (+/- 1 week), and 12 weeks (+/- 1 week) at which times all follow-up measures from the surveys will be collected. Additionally, a physical exam will be performed on every patient at every follow up appointment. The physical examination will be focusing on the mental status by asking Mini Mental State test. We will also examine the abdomen by light and deep palpation. Any deviation from the normal limits will result in un-blinding the effected patient (to elucidate whether he/she is a control or a treatment group) and withdrawal from the study. If intestinal or urinary obstruction is suspected, the appropriate imaging studies will be conducted and a consultation with the appropriate surgical service will be requested if indicated.

The following is a summery table of safety monitoring and assessments that will be conducted at every follow-up. The pregnancy test will be conducted before the start of the study and at week 6 (not included in the following table) for pre-menopausal patients.

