In terms of the blood analysis for inflammatory mediators, ten milliliter blood sample will be collected at the baseline visit, week 6 and at the end of the study (week 12) for all enrolled patients. These three time points will allow us to understand the temporal effect of sulfasalazine on inflammatory mediators. The mid-time point will allow us to maximize the data extraction in case so patients may wish to quit the study before week 12. All samples will be collected from the antecubital fossa. The blood samples will be spun at 12,000 RVM for 10 minutes and the serum will be stored in -80 degree Celsius freezer until analyzed. We will utilize commercially available enzyme-linked immunosorbent assay (ELISA) kits to measure the inflammatory mediators IL-6, and TNF-alpha. Glutamate will be measured using Amplex Red Glutamic Acid Oxidase Assay kit. Additionally, we will measure tumor markers for breast cancer including CA 27.29 and CEA using commercially available ELISA kits, we will also collect tumor measurements from standard of care PET scans to evaluate the tumor size.

The data will be analyzed when all participants complete the trial. At that point we will unblind the subjects and finalize the data analysis.

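### Does it matter that the stored biomarker blood is called plasma in one place and serum in another?

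*Protocol*

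**What the plan says.** Both statements are in the Protocol under Study Description.

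- **Paragraph on safety blood and urine samples.** "At the baseline, Week-6, and Week-12, additional blood will be immediately centrifuged", and the stored material is plasma: "the plasma will be stored in a -80 degrees Celsius freezer for later analysis for inflammatory mediators and tumor markers".
- **Paragraph on blood analysis for inflammatory mediators.** It sets the same three sampling times and a ten-millilitre sample, gives a spin speed and a ten-minute spin, and then states that "the serum will be stored in -80 degree Celsius freezer until analyzed". The analytes are IL-6 and TNF-alpha by ELISA, glutamate by an oxidase assay, and two tumor markers: "we will measure tumor markers for breast cancer including CA 27.29 and CEA using commercially available ELISA kits".

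The paragraph on follow-up visits allows either of two clinics: "The patients will return to the pain clinic or the oncology clinic for follow ups". The document does not say where the biomarker blood is processed. The Brief Summary names opioid use as primary ("The primary objective of this study is to decrease the amount of opioid pain medication use"), with pain intensity and quality of life as secondary.

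**The concern.** Plasma and serum are different sample types. The choice between them is made when the blood is drawn and cannot be undone after freezing. The two paragraphs agree on visits, storage temperature and classes of analyte, so they appear to describe the same specimen and to disagree on what it is.

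If some staff followed one paragraph and some the other, a patient could have plasma at baseline and serum at week 12. A change over time in IL-6, for example, would then contain any plasma-serum difference as well as any biological change. The Protocol gives the time course of inflammatory mediators as the reason for three draws, so that is the comparison exposed. Differences between arms would also become noisier.

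**Working it through.** The check is mainly textual; the Protocol gives no figure to reproduce.

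**1. Do the two paragraphs describe the same specimen?**

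| Feature | Safety-sample paragraph | Blood-analysis paragraph |
|---|---|---|
| Times | baseline, week 6, week 12 | baseline, week 6, week 12 |
| Handling | centrifuged at once | centrifuged for 10 minutes |
| Storage | -80 °C | -80 °C |
| Analytes | inflammatory mediators, tumor markers | IL-6, TNF-alpha, glutamate, CA 27.29, CEA |
| Stored material | plasma | serum |

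Only the last row conflicts. A split by analyte does not explain it, because the first paragraph assigns plasma to both classes of analyte that the second lists. Two separate specimens are not excluded, but neither paragraph describes a second tube or aliquot. Neither mentions an anticoagulant or a clotting step. The simplest reading is one procedure with one word used loosely.

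**2. How many results are affected?** With 40 patients and three times there are 40 × 3 = 120 planned samples, and with five analytes 120 × 5 = 600 planned results. These are the total planned biomarker output, not a count of errors. If one sample type is used throughout, the number affected is 0.

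**3. What would mixing do?** Assume a constant plasma-minus-serum difference d for an analyte. Let q be the share of plasma samples at baseline and p the share at a later visit, within an arm. The mean change in that arm shifts by d(p − q).

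- One type throughout: p = q = 0 or p = q = 1, so the shift is 0.
- Type differs by clinic, but each patient stays at one clinic: each patient's change has shift 0.
- Type varies between visits: the shift within an arm may differ from 0. The difference between arms shifts by d[(p₁ − q₁) − (p₂ − q₂)]. Assignment is random, and patients and treating physicians are blinded, so with handling unrelated to arm this has expectation 0. Chance imbalance adds noise.

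The Protocol gives no value of d for any analyte, and no basis for p or q, so no size can be calculated.

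**4. What depends on it?** None of the objectives in the Brief Summary uses these samples. The sample size of 16 evaluable per group, raised to 20 for dropout, is not linked to a biomarker.

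**The case for a change.** The best argument for requiring a change is that it is cheap and that the error, once made, is permanent. The blood is drawn by a phlebotomist from outside the study team, who depends on written instructions. Visits may take place at two clinics, and no laboratory manual is shown or mentioned. The assays also bear on the trial's rationale, which rests partly on lower inflammatory mediators and less glutamate release. Aligning the two paragraphs would need no extra sample or visit.

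Some of this stands. The contradiction is in the text, the choice of tube is irreversible, and a laboratory manual that settles it cannot be assumed to exist.

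The step from a wrong word to mixed samples does not stand. Nothing shows two processing streams: both clinics belong to one university, and the research team labels the samples. Anyone preparing the draws must choose a tube before the first patient, and the kits constrain that choice more than either paragraph does. The correction usually proposed leaves the sample type to the kits as well, so it would settle nothing that the laboratory does not have to settle anyway.

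**Conclusion.** The mismatch between plasma and serum is certain; an effect on the results is conjecture. It is a clerical slip about supporting measurements, and correcting it would alter no stated number, objective, analysis or conclusion. No change to the plan follows.

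This rests on two assumptions: that the laboratory uses one sample type per analyte at all visits and both clinics, and that handling is unrelated to treatment arm. The Protocol contains nothing against either. If the first failed, the time course of the biomarkers within an arm could be distorted by an amount that cannot be derived from the document. The randomised comparison of biomarkers would mainly lose precision, and the results on opioid use, pain intensity and quality of life would be unaffected.

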## **Double Blind Trial Investigating the Role of Sulfasalazine in Decreasing Opioids Requirements in Breast Cancer Patients**

cultural settings. This questionnaire would be collected at the start of the trial, week 2, week 4, week 6, week 8, week 10 and the end of the 12 week pilot trial.

Finally, patients will be provided with a pain medication log to document the amount of pain medications needed. Subjects will record their opioid pain medication use - both long acting and breakthrough pain. They will be asked to record their opioid pain use daily (both long acting and breakthrough pain meds). In addition, we will also capture data regarding NSAID's, Tylenol and other medications used for pain and document the daily study medication. A research nurse or study coordinator will make weekly calls to the patient to ensure they are taking assigned drug (placebo or sulfasalazine), assess side effects, and recording pain medication use. At the end of study, the drug diary will be collected. Due to the subjective of pain, we chose verified and well accepted surveys that are used in clinical settings to have a more relevant data for better interpretation.

All surveys will be conducted at baseline before starting any treatment. The pain medication log will be done on daily basis. At the end of the study, all data will be gathered and compiled for statistical analysis. The study will be conducted at both the pain clinic at south campus and at the oncology clinic at main campus.

In terms of the blood analysis for inflammatory mediators, ten milliliter blood sample will be collected at the baseline visit, week 6 and at the end of the study (week 12) for all enrolled patients. These three time points will allow us to understand the temporal effect of sulfasalazine on inflammatory mediators. The mid-time point will allow us to maximize the data extraction in case so patients may wish to quit the study before week 12. All samples will be collected from the antecubital fossa. The blood samples will be spun at 12,000 RVM for 10 minutes and the serum will be stored in -80 degree Celsius freezer until analyzed. We will utilize commercially available enzyme-linked immunosorbent assay (ELISA) kits to measure the inflammatory mediators IL-6, and TNF-alpha. Glutamate will be measured using Amplex Red Glutamic Acid Oxidase Assay kit. Additionally, we will measure tumor markers for breast cancer including CA 27.29 and CEA using commercially available ELISA kits, we will also collect tumor measurements from standard of care PET scans to evaluate the tumor size.

The data will be analyzed when all participants complete the trial. At that point we will unblind the subjects and finalize the data analysis.

### **Inclusion Criteria:**

- Adult patients aged >18 and 95< year old.
- Diagnosis of cancer with 3-day average numeric pain rating score (NPRS) for pain of at least 5/10 at baseline evaluation.
- On opioid regimen for at least 3 weeks. This time frame will allow patients to have a stable opioid regimen as it typically takes a few weeks of titration of opioids to reach

## **Double Blind Trial Investigating the Role of Sulfasalazine in Decreasing Opioids Requirements in Breast Cancer Patients**

an acceptable dosing. Having a stable opioid regimen will allow us to better be able to interpret the effects of sulfasalazine.

- Pain duration of at least 6 weeks or more.
- Prognosis greater than 6 months
- Able to take oral medication.

### **Exclusion Criteria:**

- Patients with intestinal or urinary obstruction or at risk of such disorders.
- History of porphyria
- History of blood dyscrasias, hepatic disease (ALT and AST greater than 2.5X the upper limit of normal).
- History renal disease (serum creatinine greater than 1.5 mg/dl)
- Patients taking Lapatinib or Digoxin.
- No sustained hypercalcemia (blood calcium level greater than 10.4 mg/dl).
- Hypersensitivity to sulfasalazine, its metabolites, sulfonamides, or salicylates.
- The patient is or becomes incarcerated.
- History of addictive behavior, severe clinical depression, or psychotic features.
- Possible pregnancy or lactation.
- Those receiving remuneration for their pain treatment (e.g., disability, worker's compensation).
- Those involved in active litigation relevant to their pain.

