## **Double Blind Trial Investigating the Role of Sulfasalazine in Decreasing Opioids Requirements in Breast Cancer Patients**

patient first receives the assigned treatment. Each patient will have 7 clinic visits that are related to the study. Initially, we will conduct urine pregnancy test before the start of the study and at week 6 except for patients with documented hysterectomies. If a patient suspects she may be pregnant, additional urine pregnancy test will be conducted. If the results suggest possible pregnancy, the patient will be excluded from the study.

Patients with breast cancer-induced bone pain will be identified and recruited from the chronic pain clinic and from the oncology clinic at the University of Arizona. The consent process as well as the pain evaluation will be conducted at the Chronic Pain clinic at South Campus or at the oncology clinic at main campus. Patients that meet our inclusion criteria and consent to the study will be randomized into either a placebo (sugar pill) or sulfasalazine group. We estimate that a sample size of 16 subjects per group will be necessary based on the power calculations shown below. Because not all subjects will complete the study and provide evaluable data, we will enroll 20 subjects per group. Forty patients will be stratified according to age and randomly assigned to either a placebo or active treatment group in a 1:1 ratio. The randomization sequence will be generated by the Biostatistics Shared Resource of UACC using a computer-generated process. The assignment of patients will be revealed only to the pharmacist. The pharmacist will also not be involved in communicating with patients or analyzing the data. Neither the patients nor the treating physicians will know into which group individual patients will be assigned. Initially, all patients will be given written surveys designed to assess for opioid use, pain level, and quality of life.

The treatment group will receive supplies for 3 months of sulfasalazine at an initial dose of 0.5 gram three times a day for a week then at a dose of 1 gram three times a day for the remainder of the 3 months. Patients will be asked to take their medications with every meal (assuming three meals a day) in addition to their regular pain medications. The placebo group will be asked to take capsules filled with cornstarch three times a day in a similar manner.

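### The calcium exclusion is worded with reversed polarity, and the upper age limit has its sign on the wrong side: two small corrections to operative entry rules

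*Protocol*

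**What the plan says.** Under the heading "Exclusion Criteria" the Protocol gives 12 bullets. The first is typical: "Patients with intestinal or urinary obstruction or at risk of such disorders". The sixth concerns calcium and reads "No sustained hypercalcemia (blood calcium level greater than 10.4 mg/dl".

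Under Inclusion Criteria, the first bullet sets the age limits: "Adult patients aged >18 and 95< year old".

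The Protocol gives no other calcium limit for entry and does not restate the age limits. The study description says that randomisation is stratified by age, and it lists a basic metabolic panel among the safety assessments, but neither statement carries an eligibility limit.

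**The concern.** An exclusion list works by one convention: if the statement is true of a patient, the patient does not enter. A bullet that states the absence of a condition turns that convention round. For calcium, the patients the bullet was evidently meant to keep out are the ones it lets pass, and patients with normal values meet a listed exclusion.

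What is at stake is the record of eligibility. Entry criteria are commonly copied to a screening form and checked against the text. If that happens here, a normal-calcium patient enrolled in line with the obvious intent would still meet a written exclusion and could be recorded as a deviation. Conversely, the text gives no ground for refusing a patient with sustained hypercalcaemia.

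The age line is a secondary matter of the same kind. A sign placed after 95 does not state an upper limit as it stands.

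**Working it through.** No formula applies, and the Protocol states no figure to reproduce. The check is one of logic: take each line, apply the convention of its own list, and see who passes.

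**Inputs**

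- Protocol, Exclusion Criteria, sixth bullet: absence of sustained hypercalcaemia, with a cut-off of 10.4 mg/dl.
- Protocol, Exclusion Criteria, the other 11 bullets: obstruction, porphyria, blood dyscrasias or hepatic disease, renal disease, two named drugs, hypersensitivity, incarceration, psychiatric or addiction history, pregnancy or lactation, remuneration, litigation. Each bars entry by being present.
- Protocol, Inclusion Criteria, first bullet: the age line.

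**Calcium.** Convention: statement true means excluded. The calcium values are illustrative.

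| Patient | Is the statement true as written? | Result as written | Result with No deleted |
|---|---|---|---|
| Calcium 9.5 mg/dl | Yes | Excluded | Not excluded by this line |
| Sustained calcium 12 mg/dl | No | Not excluded by this line | Excluded |

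Deleting one word reverses both rows. No other line of the list would catch the second patient on account of calcium.

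**Age.** Convention: statement true means eligible on this point. Read symbol by symbol, the line requires age > 18 and 95 < age. For a 60-year-old, 60 > 18 is true and 95 < 60 is false, so the line fails. Read as a range with a misplaced sign, it is 18 < age < 95, and the 60-year-old passes. The line names a lower and a higher number joined as a pair, so the second reading is plainly the intended one.

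**Effect on the statistics.** The Protocol's sample-size statement, "We estimate that a sample size of 16 subjects per group will be necessary based on the power calculations shown below", is not an input to either line, and correcting them leaves it as it is.

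**The case against.** The strongest reply is that nobody would apply these lines literally. The calcium bullet stands among safety exclusions and carries its own upper cut-off, so only one intent is plausible. Taken together, the two literal readings would admit only patients over 95 with sustained hypercalcaemia, which is absurd enough to protect against itself. Recruitment runs through two clinics of one institution, not many independent sites, and the Protocol contains no screening checklist on which a literal reading could be shown to operate.

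Most of this stands, and it limits the point. A reader might infer that the trial will select the opposite of its intended population, or that all 40 planned patients are affected. The document does not support that. It is a consequence of literal reading only, not a forecast of enrolment.

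Three further inferences also go too far:

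- That only patients over 95 qualify. This ignores that the age line is written as a range.
- That a lower bound of >18 contradicts the word adult. A protocol may set its lower limit above 18, so the bound is coherent.
- That the word sustained must be defined, dropped or tied to a repeat sample. It describes persistence while the parenthesis gives the level, and the two do not conflict. Changing it would alter the substance of the criterion, and a confirmatory sample would add a procedure.

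What the reply does not remove is the wording itself. The calcium bullet says the opposite of what the list needs, and nothing elsewhere puts it right. An entry rule should not depend on the reader assuming its contrary.

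**Conclusion.** The calcium exclusion is wrong as written. Followed literally, it bars normal-calcium patients and does not bar those with sustained hypercalcaemia. The age line has its upper sign on the wrong side of 95 and is a secondary point.

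Severity is low, because the intent of both lines can be inferred. The conclusion rests on two things: the ordinary convention that a true statement in an exclusion list excludes, which the other 11 bullets follow; and the absence of any other calcium rule for entry in the Protocol. It does not depend on the statistical analysis plan, which is not at hand, since eligibility is fixed in the Protocol. Design, power and analysis are unaffected.

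**What to change.** In the Protocol's Exclusion Criteria, delete the word No at the start of the calcium bullet, so that it names sustained hypercalcaemia as the excluding condition. Leave the 10.4 mg/dl threshold and the word sustained unchanged.

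In the same amendment, write the age limits in the Inclusion Criteria as >18 and <95 years, keeping the lower bound as it is.

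The cost is a two-line wording amendment, with the same correction to any screening form that copies these lines. It adds no visit, sample or procedure.
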